8.6. Hospitalization

Hospitalization is defined as any initial admission (even less than 24 hours) in a hospital or equivalent healthcare facility or any prolongation of an existing admission. Admission also includes transfer within the hospital to an acute/intensive care unit (eg, from the psychiatric wing to a medical floor, medical floor to a coronary care unit, or neurological floor to a tuberculosis unit). An emergency room visit does not necessarily constitute an hospitalization; however, the event leading to the emergency room visit should be assessed for medical importance.

Hospitalization does not include the following:

- Rehabilitation facilities;
- Hospice facilities;
- Respite care (eg, caregiver relief);
- Skilled nursing facilities;
- Nursing homes;
- Same day surgeries (as outpatient/same day/ambulatory procedures).

Hospitalization or prolongation of hospitalization in the absence of a precipitating, clinical AE is not in itself an SAE. Examples include:

- Admission for treatment of a preexisting condition not associated with the development of a new AE or with a worsening of the preexisting condition (eg, for work-up of persistent pre-treatment laboratory abnormality);
- Social admission (eg, subject has no place to sleep);
- Administrative admission (eg, for yearly physical examination);
- Protocol-specified admission during a study (eg, for a procedure required by the study protocol);

- Optional admission not associated with a precipitating clinical AE (eg, for elective cosmetic surgery);
- Hospitalization for observation without a medical AE;
- Pre-planned treatments or surgical procedures. These should be noted in the baseline documentation for the entire protocol and/or for the individual subject.

Diagnostic and therapeutic non-invasive and invasive procedures, such as surgery, should not be reported as AEs. However, the medical condition for which the procedure was performed should be reported if it meets the definition of an AE. For example, an acute appendicitis that begins during the AE reporting period should be reported as the AE, and the resulting appendectomy should be recorded as treatment of the AE.

8.7. Severity Assessment

Adverse events occurring during this study will be graded in accordance with the Grade 1 to Grade 5 scale presented below. The detailed definitions are in accordance with National Cancer Institute Common Terminology Criteria for Adverse Event (CTCAE) Version 4.03. Documentation of AE grading in the source documents and CRF must be consistent with provided definitions.

GRADE	Clinical Description of Severity
0	No Change from Normal or Reference Range (This grade is not included in the Version 4.03 CTCAE document but may be used in certain circumstances).
1	MILD Adverse Event
2	MODERATE Adverse Event
3	SEVERE Adverse Event
4	LIFE-THREATENING consequences; urgent intervention indicated
5	DEATH RELATED TO Adverse Event

Note the distinction between the severity and the seriousness of an AE. A severe event is not necessarily an SAE. For example, a headache may be severe (interferes significantly with the subject's usual function) but would not be classified as serious unless it met one of the criteria for SAEs, listed above.

8.8. Causality Assessment

The investigator's assessment of causality must be provided for all AEs (serious and non-serious); the investigator must record the causal relationship in the CRF/DCT, as appropriate, and report such an assessment in accordance with the serious adverse reporting requirements if applicable. An investigator's causality assessment is the determination of whether there exists a reasonable possibility that the investigational product caused or contributed to an AE; generally the facts (evidence) or arguments to suggest a causal

relationship should be provided. If the investigator does not know whether or not the investigational product caused the event, then the event will be handled as “related to investigational product” for reporting purposes, as defined by the Sponsor (see Section on [Reporting Requirements](#)). If the investigator's causality assessment is “unknown but not related to investigational product”, this should be clearly documented on study records.

In addition, if the investigator determines that an SAE is associated with study procedures, the investigator must record this causal relationship in the source documents and CRF/DCT, as appropriate, and report such an assessment in accordance with the SAE reporting requirements, if applicable.

8.9. Exposure During Pregnancy

For both unapproved/unlicensed products and for marketed products , an Exposure During Pregnancy (EDP) occurs if:

1. A female becomes, or is found to be, pregnant either while receiving or having been exposed (eg, because of treatment or environmental exposure) to the investigational product; or the female becomes, or is found to be pregnant after discontinuing and/or being exposed to the investigational product.

An example of environmental exposure would be a case involving direct contact with a Pfizer product in a pregnant woman (eg, a nurse reports that she is pregnant and has been exposed to chemotherapeutic products).

2. A male has been exposed (eg, because of treatment or environmental exposure) to the investigational product prior to or around the time of conception and/or is exposed during his partner's pregnancy.

If a study subject or study subject's partner becomes or is found to be pregnant during the study subject's treatment with the investigational product, the investigator must submit this information to the Pfizer Drug Safety Unit on a Serious Adverse Event (SAE) Report Form and Exposure During Pregnancy (EDP) supplemental form, regardless of whether an SAE has occurred. In addition, the investigator must submit information regarding environmental exposure to a Pfizer product in a pregnant woman (eg, a subject reports that she is pregnant and has been exposed to a cytotoxic product by inhalation or spillage) using the EDP Supplemental Form. This must be done irrespective of whether an AE has occurred and within 24 hours of awareness of the exposure. The information submitted should include the anticipated date of delivery (see below for information related to termination of pregnancy).

Follow-up is conducted to obtain general information on the pregnancy and its outcome for all EDP reports with an unknown outcome. The investigator will follow the pregnancy until completion or until pregnancy termination and notify Pfizer of the outcome as a follow up to the initial EDP supplemental Form. In the case of a live birth, the structural integrity of the neonate can be assessed at the time of birth. In the event of a termination, the reason(s) for termination should be specified and, if clinically possible, the structural integrity of the

terminated fetus should be assessed by gross visual inspection (unless pre-procedure test findings are conclusive for a congenital anomaly and the findings are reported).

If the outcome of the pregnancy meets the criteria for an SAE (ie, ectopic pregnancy, spontaneous abortion, intrauterine fetal demise, neonatal death, or congenital anomaly [in a live born baby, a terminated fetus, an intrauterine fetal demise or a neonatal death]), the investigator should follow the procedures for reporting SAEs.

Additional information about pregnancy outcomes that are reported as SAEs follows:

- “Spontaneous abortion” includes miscarriage and missed abortion;
- Neonatal deaths that occur within 1 month of birth should be reported, without regard to causality, as SAEs. In addition, infant deaths after 1 month should be reported as serious adverse events when the investigator assesses the infant death as related or possibly related to exposure to the investigational product.

Additional information regarding the EDP may be requested by the investigator. Further follow-up of birth outcomes will be handled on a case-by-case basis (eg, follow-up on preterm infants to identify developmental delays). In the case of paternal exposure, the investigator will provide the study subject with the Pregnancy Partner Release of Information Form to deliver to his partner. The Investigator must document in the source documents that the subject was given the Pregnancy Partner Release of Information Form to provide to his partner.

8.10. Occupational Exposure

An occupational exposure occurs when during the performance of job duties, a person (whether a healthcare professional or otherwise) gets in unplanned direct contact with the product, which may or may not lead to the occurrence of an adverse event.

An occupational exposure is reported to the drug safety unit within 24 hours of the Investigator's awareness, using the SAE Report form, regardless of whether there is an associated AE/SAE. Since the information does not pertain to a subject enrolled in the study, the information is not reported on a Case Report Form (CRF), however a copy of the completed SAE Report form is maintained in the investigativesite file.

8.11. Withdrawal Due to Adverse Events

Withdrawal due to AE should be distinguished from withdrawal due to other causes, according to the definition of AE noted earlier, and recorded on the appropriate AE CRF/DCT page.

When a subject withdraws because of an SAE, the SAE must be reported in accordance with the reporting requirements defined below.

8.12. Eliciting Adverse Event Information

The investigator is to report all directly observed AEs and all AEs spontaneously reported by the study subject. In addition, each study subject will be questioned about AEs.

8.13. Reporting Requirements

Each AE is to be assessed to determine if it meets the criteria for SAEs. If an SAE occurs, expedited reporting will follow local and international regulations, as appropriate.

8.13.1. Serious Adverse Event Reporting Requirements

If an SAE occurs, Pfizer is to be notified within 24 hours of investigator awareness of the event.

In particular, if the SAE is fatal or life-threatening, notification to Pfizer must be made immediately, irrespective of the extent of available AE information. This timeframe also applies to additional new information (follow-up) on previously forwarded SAE reports as well as to the initial and follow-up reporting of exposure during pregnancy, exposure via breastfeeding and occupational exposure cases.

In the rare event that the investigator does not become aware of the occurrence of an SAE immediately (eg, if an outpatient study subject initially seeks treatment elsewhere), the investigator is to report the event within 24 hours after learning of it and document the time of his or her first awareness of the AE.

For all SAE, the investigator is obligated to pursue and provide information to Pfizer in accordance with the timeframes for reporting specified above. In addition, an investigator may be requested by Pfizer to obtain specific additional follow-up information in an expedited fashion. This information collected for SAEs is more detailed than that captured on the AE CRF/DCT. In general, this will include a description of the AE in sufficient detail to allow for a complete medical assessment of the case and independent determination of possible causality. Information on other possible causes of the event, such as concomitant medications, vaccines, and/or illnesses must be provided. In the case of a subject death, a summary of available autopsy findings must be submitted as soon as possible to Pfizer or its designated representative.

8.13.2. Non-Serious Adverse Event Reporting Requirements

All AEs will be reported on the AE page(s) of the CRF/DCT. It should be noted that the form for collection of SAE information is not the same as the AE CRF/DCT. Where the same data are collected, the forms must be completed in a consistent manner. For example, the same AE term should be used on both forms. AE should be reported using concise medical terminology on the CRFs/DCTs as well as on the form for collection of SAE information.

8.13.3. Sponsor's Reporting Requirements to Regulatory Authorities

Adverse event reporting, including suspected unexpected serious adverse reactions, will be carried out in accordance with applicable local regulations.

9. DATA ANALYSIS/STATISTICAL METHODS

Detailed methodology for summary and statistical analyses of the data collected in this study will be documented in a Statistical Analysis Plan, which will be maintained by the sponsor. This document may modify the plans outlined in the protocol; however, any major modifications of the primary endpoint definition and/or its analysis will also be reflected in a protocol amendment.

9.1. Sample Size Determination

This study is exploratory in nature; no pre-planned hypothesis testing is to be performed. The sample size determination is not based on statistical power considerations. Dose cohort size in the SAD portion is generally 8 subjects with a 6:2 ratio of active drug to placebo in a randomized manner and generally 10 subjects with a 8:2 ratio of active drug to placebo in a randomized manner in the MAD portion. Additional subjects may be added at a dose level to further evaluate safety and/or tolerability after discussions between the Pfizer study team and the investigators.

The table below provides the probability of observing 2 or more SAEs under various SAE rates giving the number of subjects to be treated in a cohort in a single ascending dose cohort, and multiple-dose cohort, respectively.

Table 10. Probability of Observing 2 or More SAEs

SAE rate	Prob(X >= 2 SAEs SAE Rate, n=6)	Prob(X >= 2 SAEs SAE Rate, n=8)
0.10	0.11	0.19
0.15	0.22	0.34
0.20	0.34	0.50
0.25	0.47	0.63
0.30	0.58	0.74
0.33	0.65	0.80
0.4	0.77	0.89

9.2. Efficacy Analysis

Efficacy analysis is not applicable to this study.

9.3. Pharmacokinetic Analysis

The pharmacokinetic (PK) concentration population is defined as all enrolled subjects treated who have at least 1 concentration value.

The PK parameter analysis population is defined as all enrolled subjects treated who have at least 1 of the PK parameters of interest.

9.3.1. Derivation of Pharmacokinetic Parameters

PK parameters following single and multiple-dose administration will be derived from the concentration-time profiles as appropriate as follows:

Single Dose PK Parameters

Parameter	Definition	Method of Determination
AUC _{last}	Area under the serum concentration-time profile from time zero to the time of the last quantifiable concentration (C _{last})	Linear/Log trapezoidal method
AUC _{inf} ^a	Area under the serum concentration-time profile from time zero extrapolated to infinite time	AUC _{last} + (C _{last} */k _{el}), where C _{last} * is the predicted serum concentration at the last quantifiable time point estimated from the log-linear regression analysis.
C _{max}	Maximum serum concentration	Observed directly from data
T _{max}	Time for C _{max}	Observed directly from data as time of first occurrence
t _{1/2} ^a	Terminal elimination half-life	Ln(2)/k _{el} , where k _{el} is the terminal phase rate constant calculated by a linear regression of the log-linear concentration-time curve. Only those data points judged to describe the terminal log-linear decline will be used in the regression.
CL/F ^{a,b}	Apparent clearance	Dose / AUC _{inf}
V _z /F ^{a,b}	Apparent volume of distribution	Dose / (AUC _{inf} * k _{el})
CL ^{a,c}	Clearance	Dose / AUC _{inf}
V _{ss} ^{a,c}	Steady-state volume of distribution	CL * MRT, where MRT is the mean residence time calculated as (AUMC _{inf} /AUC _{inf} - Infusion duration/2); AUMC _{inf} is area under the moment curve from time 0 extrapolated to infinity
AUC _{last(dn)}	Dose normalized AUC _{last}	AUC _{last} / Dose
AUC _{inf(dn)} ^a	Dose normalized AUC _{inf}	AUC _{inf} / Dose
C _{max(dn)}	Dose normalized C _{max}	C _{max} / Dose

^a If data permit

^b SC cohorts only

^c IV cohort only

Multiple Dose PK Parameters

Parameter	Day(s)	Definition	Method of Determination
AUC _τ	1, 57	Area under the concentration-time profile from time zero to time tau (τ), the dosing interval, where τ = 4 weeks (672 hours)	Linear/Log trapezoidal method
C _{max}	1, 57	Maximum serum concentration	Observed directly from data
C _{av}	1, 57	Average concentration	AUC _τ /τ
T _{max}	1, 57	Time for C _{max}	Observed directly from data as time of first occurrence
CL/F	1, 57	Apparent clearance	Dose / AUC _τ
C _{min}	57	Lowest concentration observed during the dosing interval	Observed directly from data
t _{1/2} ^a	57	Terminal elimination half-life	Ln(2)/k _{el} , where k _{el} is the terminal phase rate constant calculated by a linear regression of the log-linear concentration-time curve. Only those data points judged to describe the terminal log-linear decline will be used in the regression.
V _z /F ^a	57	Apparent volume of distribution	Dose / (AUC _τ / k _{el})
R _{ac}	57	Observed accumulation ratio based on AUC	AUC _τ Day 57 / AUC _τ Day 1
R _{ac,Cmax}	57	Observed accumulation ratio based on C _{max}	C _{max} Day 57 / C _{max} Day 1
AUC _{τ(dn)}	1, 57	Dose normalized AUC _τ	AUC _τ / Dose
C _{max(dn)}	1, 57	Dose normalized C _{max}	C _{max} / Dose
C _{min(dn)}	57	Dose normalized C _{max}	C _{min} / Dose

^a If data permit

Note: Actual PK sampling times will be used in the derivation of PK parameters.

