- Weight measure in gown, undergarments and socks (or in comparable standard garments used by the CRU) while fasting and empty bladder. Height measured with wall-mounted stadiometer at screening only in stocking feet and carried forward.
- Vital signs: blood pressure, pulse, temperature. Only blood pressure should be collected in triplicate. On dosing days obtain at prior to dose and at 1, 2, and 4 hours after dosing.
- Screening labs include FSH in women only, TSH, C-peptide, HIV, hepatitis B surface antigen, hepatitis B core antibody, hepatitis C antibody.
- Subjects will continue to be monitored, at approximately 1-3 month intervals, for up to 9 months beyond the last scheduled visit, if necessary, for elevated glucagon levels and/or presence of anti-PF-06293620 antibodies.
- Samples for MMTT assessment should be collected prior to the MMTT (0 minutes/fasting) and after the start of the liquid meal at 15, 30, 60, 120, 180 and 240 minutes. Blood glucose, C-peptide, insulin, glucagon and GLP-1 will be measured at all timepoints.

- f. Fingersticks with glucometer measurements to be taken before breakfast (fasting), 2-hr post-breakfast, before lunch, 2-hr post-lunch, before dinner, 2-hr post-dinner, prior to snack (between 9 and 10 PM) and then at 0300 and before breakfast (fasting) the following days (Day 1, Day 9 and Day 65). Days 9 and 65 are done as outpatient, at home.
- g. PK: on dosing days, PK sample will be collected at hours 0 (predose), 1 and 4 hours post dose.
- h. Perform injection site assessment immediately after injection, 15 minutes, 30 minutes, 1 hour, and 2 hours post administration. Additional assessments should be performed as needed after the last assessment of 2 hrs post-dose on dosing days.
- i. Subject to be questioned about compliance with metformin.
- j. Triplicate ECG: All ECG will be submitted to Central ECG vendor for independent review. On dosing days, collect triplicate ECG prior to study drug administration (pre-dose) and 1, 2, and 4 hours after dosing.
- k. Fasting plasma glucose, glucagon and GLP-1 are not collected on days when MMTT are performed – these analytes will be captured as part of the MMTT Time 0/fasting timepoint.

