9.3.2. Statistical Methods of PK Analysis

The serum PK parameters for RN909 (PF-06293620) will be summarized descriptively by dose and route of administration. Serum concentrations will be listed and summarized descriptively by dose, nominal PK sampling time and route of administration. Individual subject, summary profiles (mean and median plots) of the serum concentration-time data will be plotted by treatment and PK sampling time. For summary statistics and summary plots, the nominal PK sampling time will be used. For individual subject plots, the actual PK sampling time will be used, whilst the pre-dose time will be set to zero. Summary plots will be presented on both linear-linear and log-linear scales.

Dose normalized parameters for RN909 (PF-06293620) will be plotted against dose and route of administration and will include individual subject values and the geometric means for each dose. For SAD, AUC_{inf}, AUC_{last}, and C_{max} will be plotted; for MAD, AUC_τ and C_{max} (Day 1 and Day 57) and C_{min} (Day 57) will be plotted. These plots will be used to help understand the relationship between the PK parameters and dose.

Absolute bioavailability (F) will be estimated as the ratio of dose-normalized adjusted geometric means for SC and IV for AUC_{last} and AUC_{inf} . Dose-normalized natural log transformed AUC_{inf} (data permitting) and AUC_{last} will be analyzed using a mixed effect model with treatment as fixed effects and subject as a random effect using a one-way analysis of variance (ANOVA). Estimates of the adjusted mean differences (Test-Reference) and corresponding 90% confidence intervals will be obtained from the model. The adjusted mean differences and 90% confidence intervals for the differences will be exponentiated to provide estimates of the ratio of adjusted geometric means (Test/Reference) and 90% confidence intervals for the ratios. SC doses are the Test treatments, and IV is the Reference treatment.

Subjects having positive ADAs will be analyzed separately to assess the effects of ADAs on RN909 (PF-06293620) concentrations. If there is no effect on the concentration versus time profiles, then these subjects will be included in the descriptive statistics of concentrations and PK parameters.

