8.3. Pharmacokinetic and Pharmacodynamics Endpoint

8.3.1. PK Endpoints

The following PK parameters (if possible) in Table 2 (SAD Cohorts) and Table 3 (MAD Cohorts) will be calculated for PF-06293620 from the serum concentration-time data using standard noncompartmental methods in Table 4 and [Table 5](#).

Table 4. PK Parameters for SAD Cohorts

PK Parameter	Analysis Scale	PF-06293620
AUC_{inf}^*	ln	A, D
AUC_{last}	ln	A, D
C_{max}	ln	D
T_{max}	R	D
$t_{1/2}^*$	R	D
V_z/F^* (for SC dose)	ln	D
CL/F^* (for SC dose)	ln	D
V_{ss}^* (for IV dose)	ln	D
CL (for IV dose)	ln	D
$AUC_{inf}(dn)^*$	ln	D
$AUC_{last}(dn)$	ln	D
$C_{max}(dn)$	ln	D

Key: A=analyzed using statistical model, D=displayed with descriptive statistics,
ln=natural-log transformed, R=raw (untransformed), *=if data permits

Table 5. PK Parameters for MAD Cohorts

PK Parameter	Day(s)	Analysis Scale	PF-06293620
AUC _τ	1, 57	ln	D
C _{max}	1, 57	ln	D
C _{min}	1, 57	ln	D
T _{max}	1, 57	R	D
CL/F	57	ln	D
C _{av}	57	ln	D
t _{1/2} *	57	R	D
V _Z /F*	57	ln	D
R _{ac}	57	ln	D
R _{ac,Cmax}	57	ln	D
AUC _τ (dn)	1, 57	ln	D
C _{max} (dn)	1, 57	ln	D
C _{min} (dn)	57	ln	D

Key: D=displayed with descriptive statistics,
ln=natural-log transformed, R=raw (untransformed), *=if data permits; dn = dose normalized.

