10.2.3. PK Analyses

10.2.3.1. Concentrations below the limit of quantification

In all data presentations (except listings), concentrations below the limit of quantification (BLQ) will be set to zero. (In listings BLQ values will be reported as “<LLQ”, where LLQ will be replaced with the value for the lower limit of quantification.)

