10.2.3.3. Pharmacokinetic parameters

Actual PK sampling times will be used in the derivation of PK parameters.

If a PK parameter cannot be derived from a subject's concentration data, the parameter will be coded as NC (ie not calculated). (Note that NC values will not be generated beyond the day that a subject discontinues.)

In summary tables, statistics will be calculated by setting NC values to missing; and statistics will not be presented for a particular treatment if more than 50% of the data are NC. For statistical analyses (ie analysis of variance), PK parameters coded as NC will also be set to missing.

If an individual subject has a known biased estimate of a PK parameter (due for example to an unexpected event such as coughing during or immediately after inhalation before all of the drug is absorbed by the body), this will be footnoted in summary tables and will not be included in the calculation of summary statistics.

To assess the pharmacokinetics of PF-06293620, PK parameters will be listed and summarized for subjects in the PK analysis set (as defined in [Section 7](#)). Missing values will be handled as detailed above.

The PK parameters to be summarized by treatment are outlined in Table 8.

Table 8. SAD and MAD Cohorts PK Parameters:

Parameter	Summary statistics
SAD Cohort	
AUC _{inf} , AUC _{last} , C _{max} , V _z /F, V _{ss} , CL/F, CL, AUC _{inf} (dn), AUC _{last} (dn), C _{max} (dn)	N, arithmetic mean, median, cv%, standard deviation, minimum, maximum, geometric mean, geometric CV%.
T _{max}	N, median, minimum, maximum.
t _{1/2}	N, arithmetic mean, median, cv%, standard deviation, minimum, maximum.
MAD Cohorts	
AUC _τ , C _{max} , C _{min} , CL/F, C _{av} , V _z /F, R _{ac} , R _{ac,Cmax} , AUC _τ (dn), C _{max} (dn), C _{min} (dn)	N, arithmetic mean, median, cv%, standard deviation, minimum, maximum, geometric mean, geometric CV%.
T _{max}	N, median, minimum, maximum.
t _{1/2}	N, arithmetic mean, median, cv%, standard deviation, minimum, maximum.

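### Read literally, MAD Cmin is zero on Day 1 in treatment-naive subjects, so its log summary cannot be computed, and on Day 57 it mixes the troughs of two doses

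*Protocol*

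**What the plan says.** - **Definition.** The multiple-dose table in Protocol 9.3.1 gives Cmin as the "Lowest concentration observed during the dosing interval", read directly from the data, for Day 57 only. The same table defines AUCτ as the "Area under the concentration-time profile from time zero to time tau (τ), the dosing interval", with τ of 4 weeks (672 hours).
- **Sampling.** In the MAD Schedule of Activities, footnote g, "on dosing days, PK sample will be collected at hours 0 (predose), 1 and 4 hours post dose". Protocol 9.3.2 adds, for individual plots, "whilst the pre-dose time will be set to zero".
- **Days and scale.** SAP Table 5 ("PK Parameters for MAD Cohorts", section 8.3.1) lists Cmin for Days 1 and 57 on the natural-log scale. Its dose-normalised Cmin row is for Day 57 only, as are the Cmin plots in Protocol 9.3.2 and SAP 10.2.3.3.
- **Summaries.** For the group of MAD parameters that includes Cmin, SAP Table 8 asks for "N, arithmetic mean, median, cv%, standard deviation, minimum, maximum, geometric mean, geometric CV"%.
- **BLQ values.** SAP 10.2.3.1 says that in all data presentations except listings "concentrations below the limit of quantification (BLQ) will be set to zero".
- **Status.** Cmin is one of the secondary PK endpoints in Protocol 2.2.2. Neither document says whether the hour-0 sample counts towards it.

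**The concern.** A minimum over an interval that opens with a pre-dose sample does not necessarily measure the trough of the dose that opens it. Before the first dose there is no drug in a treatment-naive subject, so the Day 1 minimum is fixed in advance. Before the third dose, the sample in hand belongs to the second dose.

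Two things are at stake. One row that the SAP requires, Day 1 Cmin on the log scale, cannot be produced as specified. The other, Day 57 Cmin, does not refer to the same dose in every subject. It also feeds the plot of dose-normalised Cmin against dose, which is meant to show how trough exposure relates to dose.

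**Working it through.** The plan gives no figure for Cmin to reproduce, so the check works from the definitions and the predicted accumulation.

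**1. Day 1.** The interval runs from hour 0 to hour 672. Its first sample is pre-dose. In a treatment-naive subject that sample is BLQ and is presented as 0. No concentration can be lower, so Cmin = 0. Since ln(0) is undefined, no log-scale summary exists and the geometric mean is zero or undefined. SAP 10.2.3.3 covers parameters that cannot be derived (NC, set to missing), but it has no rule for a zero on the log scale.

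**2. Day 57, expected values.** Doses fall on Days 1, 29 and 57. The Day 57 pre-dose sample is therefore the trough of dose 2. The Day 85 sample is (85 − 57) × 24 = 672 h after dose 3.

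Inputs: predicted accumulation after three doses of 1.14 at 75 mg and about 1.4 at 150 mg (Protocol 1.3.3). Assumption: linear superposition, with x the fraction carried over one 28-day interval.

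- Accumulation: R = 1 + x + x², so x = (−1 + √(1 + 4(R − 1)))/2
- Ratio of Day 57 pre-dose to Day 85: (1 + x)/(1 + x + x²)

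| Source | x | Ratio |
|---|---|---|
| R = 1.14 (75 mg) | 0.124 | 1.1245/1.14 = 0.986 |
| R = 1.4 (150 mg) | 0.306 | 1.306/1.4 = 0.933 |
| Half-life 9 d, x = 2^(−28/9) | 0.116 | 1.116/1.129 = 0.988 |
| Half-life 18 d, x = 2^(−28/18) | 0.340 | 1.340/1.456 = 0.921 |

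The last two rows use the half-life range in Protocol 1.3.2 as a cross-check and agree with the first two. The predicted pre-dose value is about 1% below Day 85 at 75 mg and 7% below at 150 mg. No accumulation ratio is given for 50 mg.

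**3. Day 57, individual subjects.** Suppose each sample carries independent log-scale variation with a CV of 10 to 30% (an assumption). The chance that the pre-dose sample is the lower of the two is Φ(−ln(ratio)/(√2 × CV)). That is 54% down to 51% at R = 1.14, and 69% down to 56% at R = 1.4. The reported Cmin is therefore the trough of dose 2 in some subjects and of dose 3 in others.

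**4. Is excluding hour 0 enough?** Take one compartment with first-order absorption, C(t) proportional to ka/(ka − k) × (e^(−kt) − e^(−ka·t)), with k = ln 2/half-life, half-lives of 9 and 18 days, and assumed ka of 0.2 and 0.5 per day. These give peak times of 4.4 to 10.2 days, against about 4 to 10 days in Protocol 1.3.2. In relative units:

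| Half-life, ka | Day 1, 1 h | Day 29 pre-dose | Day 57, 1 h | Day 85 |
|---|---|---|---|---|
| 9 d, 0.2 | 0.008 | 0.182 | 0.212 | 0.207 |
| 9 d, 0.5 | 0.021 | 0.137 | 0.173 | 0.155 |
| 18 d, 0.2 | 0.008 | 0.417 | 0.568 | 0.609 |
| 18 d, 0.5 | 0.021 | 0.369 | 0.514 | 0.537 |

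With hour 0 removed, the Day 1 minimum moves to the 1 h sample, at 2% to 15% of the Day 29 trough. On Day 57 the 1 h sample still lies below Day 85 at the longer half-life. Only an end-of-interval definition ties the parameter to one dose in every case.

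**The case against.** **Hour 0 is not stated to count.** This stands as a description of the text. Inclusion is the literal reading of an interval from time zero and a sample labelled hour 0, and nothing excludes it. The BLQ rule is likewise written for data presentations, not for deriving parameters. If it does not reach derivation, the SAP has no rule for a Day 1 BLQ minimum, and the row is no more computable.

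**Day 1 may be a slip in one table row.** This is likely, since every other mention of Cmin by day is Day 57 only. It makes the repair easier but leaves a current instruction that cannot be carried out.

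**The consequence is small.** This also stands. All MAD PK output is descriptive, no hypothesis is tested, and no dose-escalation rule refers to Cmin.

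A reader might draw three stronger conclusions that the documents do not support:

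- *Day 57 Cmin describes the wrong dose.* This is true only in expectation. At 75 mg, the largest cohort in SAP Table 2, which sample is lower is close to a coin toss.
- *Trough information is lost.* SAP 10.2.3.4 summarises concentrations by dose, day and nominal time, with a count above the quantification limit, and SAP Table 8 already includes the median of Cmin.
- *Low-dose geometric means are inflated because BLQ troughs drop out.* The text available gives no quantification limit and no trough values, and the SAP does not say that zeros are dropped. The small n at 0.3 mg/kg in Protocol Table 2 (2 of 6) is no proxy, because n is also 0 of 6 at 6 mg/kg, the highest dose. No size can be put on this.

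**Conclusion.** The point holds in limited form and is worth correcting before database lock.

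- **Day 1:** under the literal reading, Cmin is 0 in all treatment-naive active subjects, and the log-scale summary that the SAP asks for cannot be produced. Former SAD participants, who may enter the MAD part 6 months after their single dose, are outside this statement, because the documents do not show whether their pre-dose sample would be BLQ.
- **Protocol and SAP disagree** on whether Day 1 Cmin exists.
- **Day 57:** the parameter mixes the troughs of doses 2 and 3. The expected difference between them is about 1% at 75 mg and 7% at 150 mg, assuming linear superposition and the predicted accumulation. Linearity is itself approximate, since Protocol 1.3.2 reports exposure rising slightly more than in proportion to dose and half-life lengthening with dose.

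The defect is one of definition. It gives no reason to doubt the safety conclusions or the other PK parameters.

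**What to change.** 1. In Protocol 9.3.1 and SAP Tables 5 and 8, define MAD Cmin as the end-of-interval concentration: the Day 29 pre-dose sample for dose 1 and the Day 85 sample for dose 3. Excluding only the hour-0 sample is the smaller edit, but step 4 of the working shows that it leaves the 1 h sample in play, so it would need Day 1 Cmin to be deleted and would not fully settle Day 57.
2. Either delete Day 1 Cmin from SAP Table 5 or add it to the protocol table, so that the two documents list the same days.
3. When any Cmin value is BLQ, report the number BLQ and the median, and compute no geometric mean or geometric CV% from zeros. If the sponsor wants a geometric mean in that case, the SAP should name the substitution rule. Several conventions exist and none is required here.

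The cost is wording only. Both samples are already scheduled, and no visit, blood draw or dose changes. If the name Cmin is kept with the new definition, the list of secondary endpoints in Protocol 2.2.2 can stay as it is. If the parameter is renamed, that list must change too.
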